| 11.6. Safety Oversight | 32 |
| 11.7. Clinical Monitoring..... | 33 |
| 11.8. Quality Assurance and Quality Control | 33 |
| 11.9. Data Handling and Record Keeping..... | 33 |
| 11.9.1. Data Collection and Management Responsibilities | 33 |
| 11.9.2. Study Records Retention..... | 33 |
| 11.10. Protocol Deviations..... | 34 |
| 11.11. Publication and Data Sharing Policy | 34 |
| 11.12. Conflict of Interest Policy | 34 |
| 12. Additional Considerations..... | 34 |
| 13. References | 34 |
| 14. List of Appendices..... | 36 |

Statement of Compliance

This study will be conducted in accordance with the International Conference on Harmonisation guidelines for Good Clinical Practice (ICH E6) and the Code of Federal Regulations on the Protection of Human Subjects (45 CFR Part 46). The statistical analysis plans will be consistent with guidances such as the CONSORT Statement [1] or STROBE Statement [2], ICMJE recommendations [3], the 2016 and 2019 statements of the American Statistical Association [4,5], and recommendations in *Nature* [6,7].¹ All personnel involved in the conduct of this study have completed human subjects protection training.

¹ [1] www.consort-statement.org [2] www.strobe-statement.org [3] www.icmje.org [4] Wasserstein RL, et al. (2016), The ASA's Statement on p-Values, *The American Statistician*, 70:2, 129-133 [5] Wasserstein RL, et al. (2019), Moving to a World Beyond $p < 0.05$, *The American Statistician*, 73:sup1, 1-19 [6] Amrhein, et al. (2019) Scientists rise up against statistical significance, *Nature* 567, 305-307 [7] Editorial (2019) It's time to talk about ditching statistical significance: Looking beyond a much used and abused measure would make science harder, but better. *Nature* 567, 283-283.

Abbreviations and Definitions of Terms

| Abbreviation/Acronym | Definition |
|----------------------|---|
| AE | Adverse Event/Adverse Experience |
| AED | Automated External Defibrillator |
| ATS | American Thoracic Society |
| Ave60Clr | Average Clearance at 60 minutes |
| Ave120Clr | Average Clearance at 120 minutes |
| BP | Blood Pressure |
| CC | Cough Clearance |
| CEMALB | Center for Environmental Medicine, Asthma and Lung Biology |
| CF | Cystic Fibrosis |
| CI | Confidence Interval |
| CIOMS | Council for International Organizations of Medical Sciences |
| Co57 | Cobalt 57 |
| CONSORT | Consolidated Standards of Reporting Trials |
| C/P | Central/Peripheral |
| CRF | Case Report Form |
| CRO | Contract Research Organization |
| CTCAE | Common Terminology Criteria for Adverse Events |
| DSMB | Data and Safety Monitoring Board |
| EMS | Emergency Medical Services |
| eCRF | Electronic Case Report Form |
| FDA | Food and Drug Administration |
| FEF 25-75 | Maximal Mid-Expiratory Flow Rate |
| FEV1 | Forced Expiratory Volume in one second |
| FVC | Forced Vital Capacity |
| GCP | Good Clinical Practice |
| HIPAA | Health Insurance Portability and Accountability Act |
| ICMJE | International Committee of Medical Journal Editors |
| IRB | Institutional Review Board |
| IUD | Intra Uterine Device |

| | |
|------------------|--|
| HR | Heart Rate |
| KeV | Kilo electron volts |
| LAI | Live Attenuated Influenza Vaccine |
| N | Number (typically refers to subjects) |
| MCC | Mucociliary Clearance |
| mCi | Millicurie |
| MDI | Metered Dose Inhaler |
| MMAD | Mass Median Aerodynamic Diameter |
| NHLBI | National Heart, Lung and Blood Institute |
| NIH | National Institute of Health |
| PE | Physical Exam |
| PEF | Peak Expiratory Flow |
| PFT | Pulmonary Function Test |
| PHI | Protected Health Information |
| PI | Principal Investigator |
| RR | Respiratory Rate |
| QA | Quality Assurance |
| QC | Quality Control |
| SABA | Short Acting Beta Agonist |
| SAE | Serious Adverse Event/Serious Adverse Experience |
| SD | Standard Deviation |
| SE | Standard Error |
| SOP | Standard Operating Procedures |
| SpO ₂ | Peripheral capillary oxygen saturation |
| STROBE | STrengthening Reporting of OBservational studies in Epidemiology |
| Tc99m-SC | Technetium99m - Sulfur colloid |
| uCi | Microcurie |
| UP | Unanticipated Problem |

1. Protocol Synopsis

| | |
|--------------------------|--|
| Study Title | Functional Studies of Novel Genes Mutated in Primary Ciliary Dyskinesia II: Genotype to Phenotype |
| Objectives | 
Primary To measure mucociliary clearance (MCC) in subjects with primary ciliary dyskinesia (PCD) caused by mutations in genes associated with a milder clinical phenotype and subjects with PCD caused by mutations in genes associated with a more severe clinical phenotype. To compare the 2 groups with each other and with healthy individuals.
 
Secondary To measure the effect of a short acting beta adrenergic (SABA) on MCC in subjects with PCD caused by mutations in genes associated with a milder clinical phenotype and subjects with PCD caused by mutations in genes associated with a more severe clinical phenotype.
 
Tertiary/Exploratory To measure cough clearance in subjects with PCD caused by mutations in genes associated with a milder clinical phenotype and subjects with PCD caused by mutations in genes associated with a more severe clinical phenotype.
 |
| Target Population | 
The target population is patients with PCD having confirmed mutations in genes associated with a milder clinical phenotype and subjects with PCD caused by mutations in genes associated with a more severe clinical phenotype. Subjects for this study will be recruited based on genotype.
 
Key Inclusion Criteria
 
PCD Patients
 
1. PCD subjects with mutations in genes associated with a milder clinical phenotype. This includes subjects with 2 confirmed mutations in RSPH1, RSPH9, RSPH4a, and DNAH11. This group may also include subjects with mutations in newly identified genes that are associated with a milder clinical phenotype. OR PCD subjects with mutations associated with a more severe clinical phenotype. This includes subjects with 2 confirmed mutations in DNAH5, DNAI1, CCDC39, and CCDC40. This group may also include subjects with mutations in newly identified genes that are associated with a more severe clinical phenotype.2. Age 12 - 90 years old3. Subjects of childbearing potential must be non-pregnant and non-lactating. 
Healthy Controls
 
1. ≥ 18 years old2. No pre-existing lung disease (asthma, cystic fibrosis, etc.)4. Subjects of childbearing potential must be non-pregnant and non-lactating. |

| | |
|--|--|
| | Key Exclusion Criteria 
1. Clinically severe disease (requiring oxygen; FEV1<30%)2. Currently smoking or vaping3. Radiation exposure in the past year that would cause them to exceed federal radiation safety guidelines4. Free of sino-nasal pulmonary exacerbation for 4 weeks. |
| Numbers of Participants | Number to be recruited for screening : 40 Number of eligible participants enrolled: 32 |
| Clinical Phase | I |
| Intervention | Short acting beta agonist inhaler (albuterol by metered dose inhaler) |
| Study Description | Participants will inhale aerosolized radiolabeled sulfur colloid (Tc99m-SC) and will undergo gamma scintigraphy to measure mucociliary and cough clearance (MCC/CC) of the radiolabeled particles-from the airways. During the first hour of MCC imaging subjects will attempt to avoid coughing. Subjects will then inhale 4 puffs of albuterol (90 mcg/puff via metered dose inhaler (MDI) with spacer) to assess the effect of beta-adrenergic stimulation on MCC over the second hour of MCC imaging. After the two hours of MCC imaging. Subjects will perform spirometry and directed coughing over a 30-minute period during which CC will be measured, again by gamma scintigraphy. Subjects will then rest (approximately 3.5 hours) and be scanned for 15 minutes at 6 hour post initial MCC/deposition scan. |
| Outcome Measures | Baseline MCC: Ave60Clr Change in MCC following albuterol: Ave120Clr-Ave60Clr Change in MCC following cough clearance: Ave150Clr-Ave120Clr |
| Study Duration | The entire study is expected to last up to 4 years. |
| Subject Participation Duration | Each subject's participation will last 1 day. |
| Estimated Time to Complete Enrollment | 4 years |
| Statistical Analysis Plans | Aim 1 will provide estimates of the mean and standard deviation of baseline MCC (Ave60Clr) for each group of PCD subjects. The 2 disease groups will be compared to data from healthy subjects using ANOVA followed by multiple comparisons, using the Tukey Kramer correction. Age, gender and the initial deposition C/P will be added as covariates to PCD groups in a linear regression model on MCC. In Aim 2, the change pre- to post-albuterol (Ave120Clr-Ave60Clr) will be calculated for each subject. Estimates of the mean and standard deviations will be reported for each group and compared with paired t-tests. The difference of change between the 2 groups will first be analyzed with an independent t-test. Age, gender and C/P will then be added as covariates in linear regression model. |

| | |
|--|--|
| | 
In Aim 3, the change pre- to post-cough clearance (Ave150Clr-Ave120Clr) will be calculated for each subject. Estimates of the mean and standard deviations will be reported for each group and compared with paired t-tests. The difference of change between the 2 groups will be analyzed with an independent t-test. Age, gender and C/P will then be added as covariates in linear regression model.
 
All tests will be 2-sided, with $\alpha=0.05$. Tests with p values above 0.05 will be considered inconclusive.
 |
|--|--|

2. Introduction: Background and Scientific Rationale

2.1. Background Information

Primary Ciliary Dyskinesia (PCD) is a heterogeneous genetic disease that results in impaired function of the cilia [1]. Pulmonary MCC is dependent on airway secretory cells and submucosal glands and ciliated cells to propel mucus upwards through the airways. Rates of MCC are dependent on ciliary beat frequency, hydration, and the rheologic properties of mucus [2]. Abnormalities in ciliary function causes reduction in mucociliary clearance (MCC), which contributes to mucus plugging and worsening of lung function. Due to cilia dysfunction, mucociliary clearance (MCC) and cough clearance (CC) are affected in PCD. PCD varies in phenotypic presentation and ranges from mild to severe loss of lung function. PCD patients develop airway obstruction and bronchiectasis as disease advances. While some patients present with bronchiectasis in childhood, virtually all adult patients have bronchiectasis [3]. PCD is a progressive disease causing a range of respiratory disease from poor lung function to chronic respiratory failure requiring lung transplant [3].

As more genetic mutations are discovered, milder phenotypes have been associated with mutations in certain genes. For example, it has been reported that individuals with mutations in *RSPH1* (radial spoke head homolog 1) have a milder presentation than other genes [4]. Individuals with *RSPH1* have a higher nasal nitric oxide value, decreased incidence of neonatal respiratory distress and higher FEV1 when compared to subjects with mutations in genes encoding outer dynein arm structures. In addition, cilia from subjects with mutations in *RSPH1* can have normal appearing structure and maintain an almost normal ciliary beat frequency, although they often beat in a circular pattern [5]. In contrast, mutation in other genes have been associated with a more severe clinical phenotype. For example, subjects with mutations in *CCDC39* or *CCD40* were significantly younger at diagnosis and had significantly lower percent predicted FEV1 than subjects with mutations in other genes [6].

Currently, there are no treatments that have been clinically approved specifically for PCD. In other disease processes, albuterol has been reported to improve mucociliary clearance. Laube et al reported decreased MCC in patients after lung transplant which significantly improved with administration of albuterol [7]. Additionally, beta agonists have been reported to improve ciliary beat frequency in human bronchial epithelial cells in vitro and in certain animal models [8-9]. The effect of beta agonists on MCC or CC has not been studied in those with mild or severe phenotypes of primary ciliary dyskinesia. A recent retrospective study did investigate bronchodilator response (BDR) with a SABA in patients with

PCD (adults and children), and reported a higher prevalence of BDR in adults and those with defects of the microtubule compared to younger patients and those with other defects [12].

2.2. Supporting Pilot / Unpublished Data

N/A

2.3. Scientific Rationale

We have previously reported that PCD patients with *RSPH1* mutations have a milder pulmonary phenotype and better lung function than patients with PCD caused by other mutations [3]. Further, we demonstrated that although cilia lacking *RSPH1* beat in an abnormal, circular pattern, *Rspn1*^{-/-} mice exhibited a low level of MCC [13]. This is in contrast to *Dnaic1*^{-/-} mice, who exhibit essentially immotile cilia and a complete lack of MCC [14]. In this aim, we will test the hypothesis that PCD subjects with mutations in *RSPH1* and certain other mutations that have a milder phenotype [4, 11] maintain a low level of MCC that is likely responsible for their milder disease phenotype. In addition, we will test the hypothesis that stimulating ciliary beat frequency (CBF) with a beta-agonist will increase MCC in this patient group. These studies may result in the development of new personalized treatments for this rare disease.

3. Objectives

3.1. Specific Aim 1

To estimate how MCC measurements vary in subjects with PCD caused by mutations in genes associated with mild and severe clinical phenotypes relative to healthy subjects, and compare the 3 populations in terms of Average Clearance.

3.2. Specific Aim 2

To characterize the effect of a short acting beta agonist (SABA) on MCC subjects with PCD caused by mutations in genes associated with mild and severe clinical phenotypes and compare the 2 populations in terms of change in Average Clearance.

[figure not shown]
3.3. Specific Aim 3

To characterize effect of cough clearance in subjects with PCD caused by mutations in genes associated with mild and severe clinical phenotypes and compare the 2 populations in term of change in Average Cough Clearance.

4. Study Design

*Prior to
Enrollment*

Total N: Obtain informed consent over the phone or by virtual meeting. Screen potential participants by inclusion and exclusion criteria; obtain medical history, document over the phone or by virtual meeting.

Perform screening and spirometry. Perform mucociliary (MCC) baseline measurement. Continue MCC measurement after SABA administration. Repeat spirometry followed by controlled cough maneuvers to assess cough clearance (CC). Subject will rest for approximately 3.5 hours followed by a final MCC/CC static measurement, 6 hours (\pm 30 minutes) post initial scan.

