7.4. Study Visits

Intervention/Treatment procedures for MCC (by visits)

Adverse events are assessed at each visit.

Screening Call: Approximately 48 hours before the study, patient will undergo a COVID-19 screen with the questions below:

Do you feel feverish or have a fever?

Do you have a new or worsening cough?

Do you have a new or worsening sore throat?

Are you newly short of breath?

Have you had a new onset of loss of taste or smell in the last 5 days?

Do you have new onset vomiting or diarrhea?

Do you have new onset of repeated shaking with chills not related to another medical condition?

If patient answer yes to any of the questions above, study will be cancelled.

MCC/Treatment visit: On day of the study, medical history will be updated, including any new medications or new medical history. Vital signs and baseline spirometry will be collected, and a negative urine pregnancy test will be required for all women.

Participants will inhale aerosolized radiolabeled sulfur colloid (Tc99m-SC) and will undergo gamma scintigraphy to measure mucociliary and cough clearance (MCC/CC) of the radiolabeled particles from the airways. During the first hour of MCC imaging patients will attempt to avoid coughing. Subjects will then inhale 4 puffs of albuterol (90 mcg/puff via metered dose inhaler (MDI) with spacer) to assess the effect of beta-adrenergic stimulation on MCC over the second hour of MCC imaging. After the two hours of MCC imaging, patients will perform spirometry and directed coughing over a 30-minute period during which cough clearance will be measured, again by gamma scintigraphy. Subjects will then rest (app 3.5 hours) and be scanned for 15 minutes at 6 hour (\pm 30 minutes) post initial MCC/deposition scan.

All personnel performing aerosolizing procedures (MCC scans and spirometry) will wear eye protection and N95 masks. A HEPA filter will also be placed in the room where the mucociliary scans will be performed.

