7.9. Collection and Management of Tissue Specimens

Sample Preparation: N/A

Record Keeping and Monitoring: N/A

Sample Storage and Security: N/A

8. Study Measurements and Evaluations

List variables that will be abstracted from medical charts: Medical records will be reviewed to obtain previous FEV1 measurement and to confirm concomitant medications.

Describe screening evaluation: Vital signs, including heart rate, respiratory rate, temperature and blood pressure will be collected. Oxygen saturation levels will be noted, as well as breath sounds. A brief physical examination, including but not limited to the cervical lymph nodes, eyes, ears, nose, throat, cardiovascular and respiratory systems will be performed.

Describe how measurements will be taken:

Spirometry:

This test measures the volume of air that can be exhaled and the rate of airflow during exhalation after a maximal inhalation and is performed to American Thoracic Society (ATS) guidelines. Subjects will inhale as deeply as possible, then exhale as rapidly and completely as possible into the spirometer. Measurements obtained from each maneuver include the forced vital capacity (FVC), the forced expiratory volume in the first second (FEV1), the maximal mid-expiratory flow rate (FEF 25-75%) and the peak expiratory flow (PEF). The largest FVC and FEV1, from at least 3 acceptable trials, are selected for analysis; the flow rates are selected from the trial with the largest sum of FVC and FEV1.

Albuterol Inhalation:

The subject will be instructed on the proper use of MDI Inhaler, an approved device for inhalation of albuterol. The subject will use the inhaler to administer 4 puffs of albuterol.

MCC procedures:

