9.2. Description of the Study Cohort

The study cohort will consist of 12 PCD subjects with mutations in genes associated with a mild pulmonary phenotype (RSPH1, RSPH9, RSPH4a, or DNAH11) and 12 PCD subjects with mutations in genes associated with a more severe pulmonary phenotype (DNAH5, DNAI1, CCDC39, or CCDC40). A subject with mild pulmonary phenotype will typically have later onset of respiratory symptoms, better lung function, and milder bronchiectasis [4]. The age of patients will range between 12-90 years old. Eight healthy patients will be enrolled and undergo the same MCC protocol to obtain data for comparison. All subjects following the protocol will be included in the database. Subjects not

completing the protocol will be replaced. Baseline measurements of population (age, gender, race, FEV1) will be tabulated, for the whole population and per group (mild genotype, severe genotype, healthy) using mean and standard deviation and frequencies with percentages as appropriate. Data will be plotted in graphical figures including as histograms, bar plots, and scatter plots.

9.3.Aim-Specific Plans

Aim 1: To estimate how MCC measurements vary in PCD subjects with mutations in genes that are associated with mild or severe disease, relative to healthy subjects, and compare the 3 populations in term of Average Clearance.

Aim 1 is measuring MCC in PCD subjects having confirmed mutations in genes associated with a milder clinical phenotype and subjects with PCD caused by mutations in genes associated with a more severe clinical phenotype. These measurements will be reported as estimates of the means and standard deviations of Ave60Clr for each group, with associated confidence intervals. The baseline MCC in PCD subjects with “mild genotypes” and “severe genotypes” will be compared to healthy subjects. Our expected result is that subjects with mutations in genes associated with mild disease will display lower MCC rates than healthy subjects, and subjects with mutations in genes associated with severe disease will be even lower. For this comparison, we will use an ANOVA followed by multiple comparisons, using the Tukey Kramer correction. Then, to control for other possible sources of variations, age, gender and the initial deposition C/P will be added as covariates to PCD groups in a linear regression model on MCC.

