Expected results, potential problems, and alternatives. We expect to observe a significant rate of MCC (different from 0) in the group of PCD patients with mutations in genes associated with a milder phenotype. Based on previous studies of ciliary activity in PCD subjects with mutations associated with a more severe phenotype, we expect to see little or no MCC in this group of PCD patients. Further, we expect the rate of MCC to be significantly greater in subjects in the “mild genotype” group compared to the PCD patients in the “severe genotype” group. We expect that subjects with a mild genotype will respond to albuterol with an increase in MCC while the PCD patients with the severe genotype will not. We expect that subjects with mutations in genes associated with a mild phenotype will have better cough clearance compared to subjects with mutations in genes associated with a severe phenotype. As we have performed many similar studies in the past, including studies of MCC in PCD subjects, we anticipate no technical difficulties in carrying out these studies. If there is no difference detected between the groups of PCD patients, this would suggest that the less severe clinical phenotype observed in some patients is not due to the maintenance of a low level of MCC. Nevertheless, this would be an important experimental finding, as it would indicate that some other mechanism is responsible for the difference in phenotype.

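### The plan frames residual MCC as the reason for milder PCD, but no analysis relates MCC to any disease measure in the subjects scanned, so it can support a genotype–MCC association and not a mechanism conclusion

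*Combined protocol and SAP*

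**What the plan says.** **Hypothesis.** Section 2.3 says the study will test whether subjects with RSPH1 and certain other mutations "maintain a low level of MCC that is likely responsible for their milder disease phenotype".

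**Conclusion from a null.** The expected-results paragraph of Section 9.3 says that finding no difference between the PCD groups would suggest that "the less severe clinical phenotype observed in some patients is not due to the maintenance of a low level of MCC". It goes on to attribute the phenotype difference to a different mechanism.

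**Groups.** The synopsis states: "Subjects for this study will be recruited based on genotype". The phenotype behind the label is described only as what is usual: "A subject with mild pulmonary phenotype will typically have later onset of respiratory symptoms, better lung function, and milder bronchiectasis" (Section 9.2).

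**Disease measure.** At the visit, "Vital signs and baseline spirometry will be collected" (Section 7.4). Section 8 adds: "The largest FVC and FEV1, from at least 3 acceptable trials, are selected for analysis". The only statistical use named is in Section 9.2: "Baseline measurements of population (age, gender, race, FEV1) will be tabulated, for the whole population and per group".

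**The concern.** The rationale has two links: genotype to MCC, and MCC to severity. The analyses address only the first. The second is taken from earlier reports about the genes and is not examined in the people scanned, although one relevant measurement, FEV1, is available for all of them.

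What is at stake is the interpretation, not the primary estimate. The group means of Ave60Clr stand whatever is done here. But a reader of the results could be told that a mechanism has been ruled out when no analysis bears on it directly and the only test behind the statement is a non-significant group comparison.

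**Working it through.** The plan gives no figure for an MCC–severity link, so there is none to reproduce. The check is a reading of every planned analysis, followed by what an added analysis could show.

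**Step 1. Planned analyses (synopsis; Sections 9.1–9.3)**

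| Analysis | Outcome | Explanatory variables | Disease measure? |
|---|---|---|---|
| Aim 1 ANOVA, Tukey–Kramer | Ave60Clr | three groups | no |
| Aim 1 regression | MCC | PCD group, age, gender, C/P | no |
| Aim 2 t-tests and regression | Ave120Clr − Ave60Clr | PCD group; same covariates | no |
| Aim 3 t-tests and regression | Ave150Clr − Ave120Clr | PCD group; same covariates | no |
| Cohort table | age, gender, race, FEV1 | group | FEV1, descriptive only |

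Scatter plots are mentioned in Section 9.2 without naming variables. FEV1 otherwise serves eligibility and safety. No bronchiectasis or symptom severity score is collected.

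**Step 2. How informative would a null be?** Section 9.6 gives the inputs: healthy 14.3 ± 7.2, mild 3.6 ± 2, severe 0.5 ± 0.25. Group sizes of 8, 12 and 12 are from Section 9.2. The pooled SD is √[(7×7.2² + 11×2² + 11×0.25²)/29] = √(407.57/29) = 3.75, dominated by the healthy group. Simulating the planned Tukey–Kramer test (normal data, 20,000 runs) gives power of about 0.31 for mild versus severe. A separate Welch test with 12 per group would have power above 0.99. So under the plan's own assumptions the ANOVA comparison could well be null when the difference is real. The regression, if fitted to PCD subjects only, would not carry the healthy-group SD.

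**Step 3. What an MCC–FEV1 estimate could show.** The Fisher z approximation at two-sided 0.05 and 80% power is: detectable r = tanh[(1.96 + 0.84)/√(n − 3 − k)], with k covariates.

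- 24 PCD subjects, k = 0: tanh(2.80/√21) = 0.55
- plus genotype group, k = 1: tanh(2.80/√20) = 0.56
- age, gender, C/P without group, k = 3: tanh(2.80/√18) = 0.58
- group, age, gender, C/P, k = 4: tanh(2.80/√17) = 0.59
- 12 mild subjects, k = 0: tanh(2.80/√9) = 0.73
- 12 mild subjects, k = 3: tanh(2.80/√6) = 0.82

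The documents give no MCC–FEV1 correlation, so a range is shown. Unadjusted power at n = 24 is 29% for r = 0.3, 71% for 0.5 and 98% for 0.7. An observed r of 0.5 would have a 95% interval of about 0.12 to 0.75.

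**Step 4. Why genotype group must be in the model.** Take the Section 9.6 values for the two PCD groups, zero MCC–FEV1 association within either group, and an assumed 1-SD difference in FEV1 between groups. The pooled, unadjusted correlation is then significant in about 38% of simulated trials. With group included, it is significant in about 5%.

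**Step 5. Where the information lies.** With equal group sizes, the mild group's share of within-group MCC variance is 2²/(2² + 0.25²) = 4/4.0625 = 98%. A group-adjusted slope therefore rests almost wholly on the 12 mild subjects.

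**Step 6. Why no significance condition on FEV1.** A two-group t-test with 12 per group has noncentrality d×√6 on 22 df. Power is about 22%, 42% and 65% at assumed FEV1 differences of 0.5, 0.75 and 1 SD. Requiring a significant FEV1 difference would often fail through sample size alone.

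**The case against.** The case on the other side is substantial.

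- **The link is not an aim.** The objectives, the three aims and the outcome list only measure MCC and compare groups, and the tests match them. The Section 2.3 sentence is rationale, and hedged. This stands, and it is why narrowing the wording is an adequate remedy. But Section 2.3 does present the statement as a hypothesis to be tested, and Section 9.3 draws an inference from it.
- **The phenotype difference to be explained is the one already reported between genotypes.** If genotypes known to differ in severity had equal MCC, residual MCC would be a poor explanation whatever 24 FEV1 values showed. This has force as logic, but it needs evidence of equal MCC. A p value above 0.05 is not that, and Section 9.3 itself calls such a result inconclusive.
- **Age and FEV1 are tabulated by group**, so a reader can see whether the mild group is milder or older. True, though an unadjusted table with 12 per group, ages 12 to 90 and no matching does not separate genotype from age.
- **FEV1 is only one side of phenotype.** Sections 2.1 and 9.2 also cite symptom onset, bronchiectasis, neonatal distress and nasal nitric oxide. This stands as a limit on the added analysis.

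Two stronger readings are tempting. A reader might infer that the plan would declare MCC the cause after a positive result. Section 9.3 does not: for a positive result it predicts only differences in clearance. A reader might also infer that the enrolled mild group will be older, with no better lung function. The documents do not show this. The younger age in Section 2.1 is age at diagnosis, for CCDC39 and CCDC40 only, and no age gap or rate of FEV1 decline is given.

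**Conclusion.** The point holds in a limited form. The plan hypothesises, and in Section 9.3 argues from a null, about why some PCD is milder, yet no planned analysis relates MCC to any disease measure in the enrolled subjects. It supports a statement about genotype group and MCC. It does not support a statement that residual MCC does, or does not, account for milder disease.

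This is a cheap improvement and not a threat to the primary estimate. Nor would the added analysis settle the mechanism. The detectable partial correlation is about 0.59 with all covariates and 0.73 to 0.82 within the mild group, and the design is cross-sectional. These figures assume full enrolment of 24 PCD subjects and the Fisher approximation. The 98% share and the 0.31 power also assume the Section 9.6 means and SDs and normal data; the 38% assumes those values and the 1-SD FEV1 gap.

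**What to change.** 1. **Wording.** In the expected-results paragraph of Section 9.3, limit the conclusion to the association between genotype group and MCC. State that a non-significant difference between the PCD groups is inconclusive, consistent with the rule already in that section, and remove the inference to another mechanism. Soften the Section 2.3 hypothesis to match.
2. **Analysis.** Add to Aim 1, labelled exploratory and reported as estimates with 95% confidence intervals and no significance condition:
   - the difference in baseline FEV1 percent predicted between the two PCD groups, adjusted for age and gender;
   - the slope of FEV1 percent predicted on Ave60Clr in the 24 PCD subjects, with genotype group, age, gender and C/P in the model, shown alongside the estimate within the mild group alone.

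The cost is SAP wording and a few regressions on data already collected, with no new procedure or visit. The drawbacks are wide intervals, dependence on the 12 mild subjects, and a single lung-function measure standing in for phenotype. The report should state all three. If the sponsor prefers not to add the analysis, the wording change alone resolves the inconsistency.
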